110 subjects will be randomized in a 2:2:1 ratio to one of the treatment arms (canakinumab alone or canakinumab in combination with pembrolizumab or pembrolizumab alone) and receive two doses of canakinumab (200mg s.c. Q3W) alone or in combination with pembrolizumab or two doses of pembrolizumab as single agent (200mg i.v. Q3W) (Figure 3-1). Randomization will be stratified by histology (squamous vs non-squamous).. Subjects will be treated for a maximum duration of 6 weeks (2 cycles) until surgery, progression, unacceptable toxicity or discontinuation from the study treatment for any other reason. Surgery must be performed between 4 to 6 weeks after the first dose of study treatment. Delay to the surgical procedure beyond 6 weeks is acceptable, but should be avoided. The primary endpoint is the MPR rate as assessed by the percentage of subjects with $\leq 10\%$ residual viable cancer cells. The primary endpoint of MPR will be assessed centrally based on all randomized subjects, with local evaluation being a secondary endpoint. Primary analysis will be performed after all subjects have had surgical resection or have discontinued study treatment earlier due to any reason. Following the surgical procedure (or early discontinuation) subjects will not receive any further dose of study treatment. Subjects will enter in the safety follow-up period up to 130 days (i.e. canakinumab and pembrolizumab 5x half-life) after end of treatment visit.

Figure 3-1 Study design

4 Rationale

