4.2.1 Pharmacokinetics (PK) consideration

Canakinumab displays PK properties typical of an IgG1 antibody, with a mean terminal half-life of 26 days (Ilaris® USPI). Every 3 weeks dosing schedule of canakinumab is feasible based on its half-life of 26 days, and its ability to suppress CRP for at least 1 month as previously demonstrated in two single-dose phase II studies with dose ranges of 0.03 to 10 mg/kg i.v. and 25 to 300 mg s.c. (Study [CACZ885A2213] in diabetes and Study [CACZ885H2251] in gouty arthritis). Population PK analysis and simulation were also performed to compare the steady-state PK of 200 mg Q3W versus 300 mg Q4W s.c. 300 mg Q4W was selected as reference for comparison, because it is the highest approved regimen for canakinumab. As shown in [Figure 4-1](#), the simulated PK profiles of canakinumab at 200 mg Q3W and 300 mg Q4W are comparable, indicating that the safety margin with the 200 mg Q3W regimen is expected to be in line with the one from the currently approved regimen of 300 mg Q4W. Specifically, the maximum plasma concentration (Cmax) of 200 mg Q3W is not exceeding that of 300 mg Q4W.

Figure 4-1 Simulated PK profiles of canakinumab 200 mg Q3W s.c. and 300 mg Q4W s.c.

Line and band: median of individual simulated concentrations with 2.5-97.5% prediction interval.
Values reported are median (solid line) and the 95% prediction interval (shaded area, 2.5th-97.5th percentile).

[figure not shown]

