9.2 Study completion and post-study treatment

Study completion is defined as when the last subject finishes their last safety follow-up visit at 130 days after end of treatment visit and any repeat assessments associated with this visit have been documented and followed-up appropriately by the Investigator or, in the event of an early study termination decision, the date of that decision (each subject will be required to complete the study in its entirety and thereafter no further study treatment will be made available to them).

Novartis will not supply study treatment to subjects after surgery. All randomized subjects should have the last safety follow-up visit conducted 130 days after end of treatment visit. The information collected is kept as source documentation. All SAEs reported during this time period must be reported as described in [Section 10.1.3](#). Documentation of attempts to contact the subject should be recorded in the source documentation.

Primary analysis will be performed after all subjects have had surgical resection or have discontinued study treatment earlier due to any reason. The primary analysis data will be summarized in the primary clinical study report (CSR). Following the cut-off date for the analysis reported in the primary CSR, the study will remain open. Ongoing subjects will continue with safety follow-up assessments as per the schedule of assessments ([Table 8-2](#)).

The end of study defined as the earliest occurrence of one of the following: all subjects have completed or discontinued from the study.

The final analysis will occur at the end of the study. All available data from all subjects up to this cut-off date will be analyzed and summarized in a final CSR.

10 Safety monitoring and reporting

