### **2.1.3.10 On-treatment assessment/event and observation periods**

For adverse event reporting the overall observation period will be divided into three mutually exclusive segments:

1. ***pre-treatment period***: from day of subject’s informed consent to the day before first administration of study treatment
2. ***on-treatment period***: from date of first administration of study treatment to 130 days (approximately five terminal half-lives of canakinumab/pembrolizumab) after the date of last administration of study treatment
3. ***post-treatment period***: starting at day 131 after the date of last administration of study treatment

Safety summaries (tables, figures) and summaries of on-treatment death include only data from the on-treatment period with the exception of baseline data which will also be summarized where appropriate (e.g. change from baseline summaries). In addition, a separate summary for death including on treatment and post treatment deaths will be provided. In particular, summary tables for adverse events (AEs) will summarize only on-treatment events, with a start date during the on-treatment period (***treatment-emergent*** AEs).

An ***on-treatment assessment*** is defined as any assessment performed after the date of first administration of study treatment i.e. assessments performed in the following time interval (including the lower and upper limits): from date of first administration of study treatment +1 up to 130 days after the date of last administration of study treatment.

In case at time of the analysis, the date of last administration of study treatment is missing, on-treatment adverse event/assessment include any adverse event/assessment recorded in the database which occur after the start date of the study treatment.

However, all safety data (including those from the post-treatment period) will be listed and those collected during the pre-treatment and post-treatment period will be flagged.

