### **2.7.3 Laboratory data**

When analyzing laboratory related date, all sources (central and local laboratories) will be combined. The summaries will include all assessments available for the laboratory parameters collected no later than 130 days after the last study treatment administration date (see [Section](#)

**2.1.3).** Grading of laboratory values will be assigned programmatically as per NCI Common Terminology Criteria for Adverse Events (CTCAE) version 5.0.

The following summaries will be produced for hematology and biochemistry laboratory data (by laboratory parameter and treatment):

- Worst post-baseline CTC grade (regardless of the baseline status). Each subject will be counted only for the worst grade observed post-baseline.
- Shift tables using CTC grades to compare baseline to the worst on-treatment value (hypo and hyper worst grade will be summarized separately if applicable)
- For laboratory tests where CTC grades are not defined, shift tables using the low/normal/high/(low and high) classification to compare baseline to the worst on-treatment value.
- If there are multiple assessments as baseline candidate, the central lab assessment will be defined as “baseline”. If there are multiple assessments from the central lab or the local lab, the worst assessment will be defined as “baseline.”

The following listings will be produced for the laboratory data:

- Listings of all laboratory data, with CTC grades and classification relative to the laboratory normal range. Lab data collected during the post-treatment period will be flagged.
- Listing of all CTC grade 3 or 4 laboratory toxicities

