## **2.9 Secondary objective: Immunogenicity**

Immunogenicity data will be summarized using the safety set. Immunogenicity will be characterized descriptively by tabulating anti-drug antibodies (ADA) prevalence at baseline and ADA incidence on-treatment. A shift table of subjects with positive or negative anti-canakinumab and anti-pembrolizumab antibodies overall and by visit will be produced (“positive” corresponds to “worst”). A listing will be provided by subject with supporting information (i.e. ADA sample status at each timepoint (including titer for positive samples) and subject ADA status). In addition, a listing will also be provided for subjects with neutralizing antibodies (NAB) testing results. Depending on the incidence of immunogenicity, additional analysis of the effect of ADA status on PK, efficacy or safety may be performed.

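### For practically every subject who completes the schedule, the follow-up 5 canakinumab ADA sample falls outside the on-treatment window and is left out of on-treatment ADA incidence

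*SAP*

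**What the plan says.** **Window for analysis.** SAP 2.1.3.10 counts an assessment as on-treatment if it is made "from date of first administration of study treatment +1 up to 130 days after the date of last administration of study treatment", "including the lower and upper limits". SAP 2.7.3 limits the laboratory summaries to values "collected no later than 130 days after the last study treatment administration date". SAP 2.7.4.2 summarises on-treatment vital signs and flags the rest in listings. Protocol 12.5.2 uses the same anchor, the last dose, for its on-treatment period.

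**Visit schedule.** Protocol Section 3 describes a "safety follow-up period up to 130 days (i.e. canakinumab and pembrolizumab 5x half-life) after end of treatment visit". Section 9.2 states: "All randomized subjects should have the last safety follow-up visit conducted 130 days after end of treatment visit". Table 8-1 gives this visit a window of +14 days with no early side; follow-up visits 1 to 4 have ±7 days. Table 8-1 and Section 9.1.1 place the EOT visit at most 21 days after permanent discontinuation and before surgery, with no minimum lag.

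**ADA.** Protocol Table 8-5 schedules canakinumab ADA at pre-dose C1D1, pre-dose C2D1, EOT and follow-ups 1, 3 and 5. Table 8-6 ends scheduled pembrolizumab ADA at follow-up 1. SAP 2.9 characterises immunogenicity by "tabulating anti-drug antibodies (ADA) prevalence at baseline and ADA incidence on-treatment". It adds a shift table overall and by visit, and a by-subject listing.

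**The concern.** The schedule and the analysis both use 130 days but count them from different dates. Follow-up 5 runs from the EOT visit and the analysis window runs from the last dose. Because the visit cannot be early, even a short gap between last dose and EOT pushes it past the end of the window.

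At stake is a named secondary endpoint. The design collects a canakinumab ADA sample about five half-lives out, and the only definition of on-treatment assessment in the SAP then excludes it. A subject first ADA-positive at follow-up 5 would not add to on-treatment incidence, yet could appear as positive in the by-visit shift table and would appear so in the listing. The SAP does not say whether post-treatment visits enter that shift table, so the two displays could disagree.

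The same cut-off applies to other assessments at that visit. Protocol Table 8-3 puts vital signs at C1D1 and all later visits, so follow-up 5 vital signs would be listed but not summarised.

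**Working it through.** **1. The plan's own figure.** Protocol 4.2.1 describes canakinumab "with a mean terminal half-life of 26 days". 5 × 26 = 130 days, which reproduces the stated length.

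**2. Inputs, in whole days**
- L, the lag from last dose to EOT visit: 0 to 21 (Table 8-1, Section 9.1.1). This assumes discontinuation is dated at the last dose.
- Nominal day after EOT: 26, 52, 78, 104 and 130 for follow-ups 1 to 5 (Table 8-2).
- w, the visit window: −7 to +7 for follow-ups 1 to 4; 0 to +14 for follow-up 5 (Table 8-1).
- An assessment is inside the window if its day after last dose is at most 130 (SAP 2.1.3.10).

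**3. Formula.** Day after last dose = L + nominal day + w.

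| Visit | Earliest | Latest | Scheduled ADA | Inside the window? |
|---|---|---|---|---|
| Follow-up 1 | 0 + 26 − 7 = 19 | 21 + 26 + 7 = 54 | canakinumab and pembrolizumab | always |
| Follow-up 3 | 0 + 78 − 7 = 71 | 21 + 78 + 7 = 106 | canakinumab | always |
| Follow-up 4 | 0 + 104 − 7 = 97 | 21 + 104 + 7 = 132 | none (telephone call) | not relevant to ADA |
| Follow-up 5 | 0 + 130 + 0 = 130 | 21 + 130 + 14 = 165 | canakinumab | only if L = 0 and w = 0 |

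For follow-up 5 there are 22 × 15 = 330 combinations of L and w, of which 1 is inside the window. This counts combinations; it is not a probability. With L of 1 or more, the earliest possible day is 131.

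**4. How likely is L = 0?** The second dose is on Day 22 ± 3, the earliest on-schedule surgery is Day 29, and EOT biomarker blood is drawn at surgery or at most 4 days before it. If the EOT visit coincides with that draw (an assumption), a Day 22 dose gives an EOT no earlier than Day 25, so L is at least 3. L = 0 then needs a dose on Day 25 with surgery on Day 29.

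**5. In half-lives of 26 days.** The last scheduled canakinumab ADA sample that counts is at 71/26 = 2.7 to 106/26 = 4.1 half-lives after the last dose. Follow-up 5 is at 130/26 = 5.0 to 165/26 = 6.3.

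**6. Discontinuation dated after the last dose.** Take a subject dosed on Day 1 only, with discontinuation dated Day 29 (assumed), EOT 21 days later and follow-up 5 at EOT + 144. The visit is then (29 − 1) + 21 + 144 = 193 days after the last dose, so 165 is not an upper limit for every subject.

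**The case against.** The strongest reply is that the anchor is deliberate. Protocol 12.5.2 uses the same period, AE and SAE collection also run from the last dose, and five half-lives are naturally counted from there. A closing visit beyond that date ensures the window is fully observed. For AE onset this stands, and nothing here asks to change it. It does not explain why a sample scheduled for ADA should be left out of the ADA endpoint.

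Several further points stand:
- SAP 2.9 neither defines ADA incidence nor cites 2.1.3.10. The exclusion follows from reading the endpoint with the only on-treatment definition given.
- The data are not lost to the report: post-treatment results are listed and flagged, and the ADA listing gives status by timepoint.
- The SAP covers the primary CSR, whose cut-off (SAP 2.1.1) may precede some subjects' follow-up 5 in any case.
- SAP Table 2-1 keeps follow-up 5 for ECOG (EOT + 105 to EOT + 156), but the SAP treats ECOG as a non-safety assessment, so this is not a contradiction.

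A reader might infer more than the documents support:
- *That follow-up 5 never counts.* Day 130 is included, a missing last-dose date admits all later assessments (SAP 2.1.3.10), and subjects leaving early have their final assessments as soon as possible (Protocol Section 8).
- *That the laboratory summaries lose follow-up 5.* They cover hematology and biochemistry. The available text places urinalysis at that visit (Protocol 6.5.2.2) but does not show the hematology and chemistry rows of Table 8-2. The cut-off would exclude such values if they are drawn.
- *That antibody is missed because residual drug masks it before follow-up 5.* The documents say nothing about assay drug tolerance.
- *That 88 samples are lost.* That is the planned maximum (44 + 44); SAP Section 1 records that recruitment was halted.

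**Conclusion.** The mismatch is real and should be corrected. Followed as written, the SAP leaves the scheduled follow-up 5 canakinumab ADA sample out of on-treatment ADA incidence for practically every subject who completes the schedule. With discontinuation dated at the last dose, that visit falls on days 130 to 165 and is at day 131 or later whenever the EOT lag is at least one day. Pembrolizumab ADA is not affected.

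The effect on vital signs follows from the text. The effect on hematology and chemistry is conditional on those draws taking place at follow-up 5. The endpoint is descriptive and the excluded results remain in listings, so the consequence is an endpoint that ignores its own last planned sample. The documents do not allow an estimate of how many ADA-positive subjects would be missed, and the primary MPR analysis is not touched.

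**What to change.** Either of two changes would do:

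1. In SAP 2.9, define canakinumab ADA incidence over all post-baseline samples through follow-up 5, and say whether the shift table includes that visit. This is the narrower change and settles the endpoint.
2. In SAP 2.1.3.10, define on-treatment assessments, but not AE onset, as those up to the later of 130 days after the last dose and the follow-up 5 visit within its window (EOT + 144 days). Align 2.7.3 and 2.7.4.2. Do not use a fixed cap of 165 days, because it fails when discontinuation is dated after the last dose.

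Either way, record the departure in SAP Section 4, which currently reports no change to protocol-specified analyses. The cost is wording and one date derivation, with no new data collection. The downside is that assessments beyond day 130 enter the tables: up to 165 − 130 = 35 days beyond when discontinuation is dated at the last dose, and more otherwise. Under the second option, the assessment window would also differ from the AE-onset window, which table footnotes should state.

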### 2.1.3.11 Windows for multiple assessments

Time windows will be defined for descriptive summary of ECOG performance status data by visit and longitudinal data analysis. If more than one assessment is available in the same time window, the assessment closest to the planned date will be considered. If two assessments are obtained with the same time difference compared to the scheduled visit day, the assessment obtained prior to visit will be considered.

**Table 2-1 Time windows for ECOG performance status**

Time Window	Planned Visit Timing	Time Window Definition
Treatment phase		
Baseline	On or before Study Day 1*	≤ Study Day 1
Week 3	Study Day 22	Study Days 2 to end of treatment visit date ^ + 7
"Note: EOT visit data will be included if obtained within 7 days after EOT visit"		
Safety follow-up		
Safety follow-up 1	26 days from EOT	[end of treatment visit date + 8; end of treatment visit date + 52]
Safety follow-up 3	78 days from EOT	[end of treatment visit date + 53; end of treatment visit + 104]
Safety follow-up 5	130 days from EOT	[end of treatment visit date + 105; end of treatment visit + 156]

\* Study Day 1 = randomization date

^ Use end of treatment disposition date if EOT visit date is not available

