9.1 Discontinuation

9.1.1 Discontinuation of study treatment

Discontinuation of study treatment for a subject occurs when study treatment is stopped earlier than the protocol planned duration, and can be initiated by either the subject or the investigator.

The investigator must discontinue study treatment for a given subject if, he/she believes that continuation would negatively impact the subject's well-being.

Study treatment must be discontinued under the following circumstances :

- Subject/guardian decision
- Physician decision
- Pregnancy
- Any situation in which study participation might result in a safety risk to the subject
- Study terminated by sponsor

If discontinuation of study treatment occurs, the investigator should make a reasonable effort to understand the primary reason for the subject's premature discontinuation of study treatment and record this information. The investigator must register the subject's discontinuation from study treatment in the IRT system.

Subjects who discontinue study treatment or who decide they do not wish to participate in the study further should NOT be considered withdrawn from the study UNLESS they withdraw their consent (see [Section 7](#)). **Where possible, they should return for the assessments as indicated** in the Assessment Schedule. If they fail to return for these assessments for unknown reasons, every effort (e.g. telephone, e-mail, letter) should be made to contact the subject/pre-designated contact as specified in the lost to follow-up section. This contact should preferably be done according to the study visit schedule.

If the subject cannot or is unwilling to attend any visit(s), the site staff should maintain regular telephone contact with the subject, or with a person pre-designated by the subject. This telephone contact should preferably be done according to the study visit schedule.

All subjects will have an EOT visit once all drugs of the study treatment are permanently discontinued (canakinumab and/or pembrolizumab as applicable). Subjects should be scheduled for an EOT visit latest 21 days after permanent discontinuation of study treatment but before the surgery, at which time all assessments listed for EOT visit will be performed ([Table 8-2](#)). Appropriate eCRF page should be completed at this time, giving the date and reason for stopping the study treatment. EOT is not considered as end of study.

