**Table 2-5 ECOG Performance Scale**

Score	Description
0	Fully active, able to carry on all pre-disease performance without restriction
1	Restricted in physically strenuous activity but ambulatory and able to carry out work of a light or sedentary nature, e.g., light house work, office work
2	Ambulatory and capable of all self-care but unable to carry out any work activities. Up and about more than 50% of waking hours
3	Capable of only limited self-care, confined to bed or chair more than 50% of waking hours
4	Completely disabled. Cannot carry on any self-care. Totally confined to bed or chair
5	Dead

Time window for ECOG PS are defined in [Table 2-1](#). If the closest assessment to the target date has two or more ECOG filled out on the same date, then the worst ECOG PS value will be used.

Time windows are applicable for descriptive summary of ECOG data by visit only.

Frequency counts and percentages of patients in each score category will be provided by treatment arm and time point.

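### SAP Table 2-1 pools C2D1 and end-of-treatment ECOG in one Week 3 window, so the pre-surgery value is nearly always left out of the by-visit summary

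*SAP*

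**What the plan says.** SAP Table 2-1 defines the ECOG windows. After baseline, the treatment phase has one row, Week 3, planned for Study Day 22, with Study Day 1 being the randomization date. Its range is "Study Days 2 to end of treatment visit date" plus 7 days. A note adds: "EOT visit data will be included if obtained within 7 days after EOT visit". The next row, safety follow-up 1, covers "end of treatment visit date + 8; end of treatment visit date + 52". No row is named for EOT.

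SAP 2.1.3.11 sets the selection rule: "If more than one assessment is available in the same time window, the assessment closest to the planned date will be considered". When two values are equally distant, "the assessment obtained prior to visit will be considered". SAP 2.7.4.3 adds that the worst score is used when several are recorded on the selected date, and that frequencies are shown by arm and time point. It also restricts the scope: "Time windows are applicable for descriptive summary of ECOG data by visit only".

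On timing, the protocol plans C2D1 for Day 22 (Table 6-4) with a 3-day tolerance either way (Table 8-1). Section 9.1.1 asks for an "EOT visit latest 21 days after permanent discontinuation of study treatment but before the surgery". Section 3 places surgery 4 to 6 weeks after the first dose.

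**The concern.** Two visits with different meanings share one window whose target is the planned date of the first of them. C2D1 falls around the second dose. EOT is the visit scheduled after treatment has ended and before resection. With one value kept per window and the target at Day 22, the C2D1 value will usually win. The by-visit table then goes from about Day 22 to follow-up 1, planned 26 days after EOT and generally after surgery.

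The time point lost is the one that shows performance status just before the operation. The protocol summary lists ECOG among the key safety assessments, and in a neoadjuvant trial a reader will look for it there. The note to SAP Table 2-1 suggests that the authors meant EOT values to appear. In addition, a subject without a C2D1 value, for example after early discontinuation, contributes an EOT value to the row labelled Week 3, so that row mixes visits.

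**Working it through.** The plan states no figure to reproduce here. The check applies the written selection rule to every permitted combination of visit days.

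**Inputs**
- Target day: 22 (SAP Table 2-1), which agrees with 1 + 21 for a 21-day cycle.
- C2D1 day *C*: 22 ± 3, so Day 19 to 25 (protocol Tables 6-4 and 8-1).
- EOT day *E*: 1 to 21 days after C2D1. This takes the C2D1 dose as the end of treatment for a two-dose subject (protocol 9.1.1 and Table 8-1). The protocol sets no minimum gap.
- Ties go to the earlier value (SAP 2.1.3.11).

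**Where an EOT value can fall.** Follow-up 1 opens at EOT + 8 and there is no EOT row, so an EOT-visit value can only enter Week 3.

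**Rule.** EOT is kept only if |*E* − 22| < |*C* − 22|.
- If *C* ≥ 22, any later *E* is farther from 22, so C2D1 always wins.
- If *C* < 22, EOT wins only when *C* < *E* < 44 − *C*, which is 43 − 2*C* days.

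| C2D1 day | EOT days on which EOT is kept | Count |
|---|---|---|
| 19 | 20 to 24 | 43 − 38 = 5 |
| 20 | 21 to 23 | 43 − 40 = 3 |
| 21 | 22 | 43 − 42 = 1 |
| 22 to 25 | none | 0 |

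**Count.** There are 7 × 21 = 147 day pairs. EOT is kept in 5 + 3 + 1 = 9 and dropped in 147 − 9 = 138, and 138 / 147 = 94%. If C2D1 may run to Day 32 (25 plus the 7-day interruption allowed in protocol 6.5.1), there are 14 × 21 = 294 pairs and the same 9 exceptions.

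**Threshold.** The latest exception is *E* = 24. With *C* = 19 and *E* = 25 both distances are 3, and the tie keeps C2D1. From Day 25 on, an EOT value never displaces a C2D1 value.

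**Against the surgery date.** Taking the first dose as Day 1, 4 to 6 weeks later is Day 29 to 43. An EOT visit within 4 days before surgery, the limit Table 8-1 gives for EOT biomarker sampling, is no earlier than 29 − 4 = Day 25, so it always loses to an available C2D1 value. For example, with C2D1 on Day 22 and EOT on Day 36, the distances are 0 and 14.

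**With a separate EOT row.** Both values are tabulated in all 147 pairs. At present only one of the two is tabulated in each pair.

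**The case against.** The strongest reply is that little depends on this table. The windows govern only the by-visit ECOG summary, and SAP 2.1.3.10 says all safety data will be listed. ECOG is not among the safety endpoints in the objectives tables, which name adverse events, vital signs and laboratory abnormalities. Whether subjects reach surgery is measured directly by the surgical feasibility rate. All of this stands, and it sets the severity.

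The table note can also be read as only making EOT values eligible for the window, which has effect when C2D1 is missing. That reading is possible. It still leaves no pre-surgery time point for subjects with both values, and it puts EOT values under a Week 3 label.

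Three stronger readings are tempting, and the documents do not support them.
- A reader might infer that EOT is lost for every subject with a C2D1 value. The nine exceptions above show otherwise, and values on the same selected date are resolved by taking the worst.
- A reader might infer that the data are discarded. They are left out of one summary and remain in the database and listings.
- A reader might infer from the + 7 bound that post-operative values will enter the row. The EOT visit must precede surgery. With surgery no earlier than Day 29, a post-operative value inside EOT + 7 requires EOT on Day 22 or later, and a value from an EOT visit on an earlier date is then nearer the target. A later, unscheduled post-operative value could be chosen only if the nearer in-window values were missing.

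**Conclusion.** The point holds as a minor defect in descriptive safety reporting. As written, the SAP leaves the EOT pre-surgery ECOG value out of the by-visit summary for nearly every subject with a C2D1 value, and always when EOT is Day 25 or later. This sits badly with its own note that EOT data will be included. When C2D1 is missing, the EOT value appears as Week 3.

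The 94% counts possible day pairs and is not a forecast of patient frequencies. The conclusion assumes first dosing on the randomization date, as protocol 6.3.2 plans, and surgery inside the protocol window for the comparison with surgery dates. It also assumes that ECOG is recorded at both C2D1 and EOT. That is inferred from the Day 22 target and the EOT note in SAP Table 2-1, because the ECOG row of protocol Table 8-2 is not legible in the text available. For the same reason, one cannot say that EOT is the only ECOG assessment between the second dose and resection. No endpoint, estimand or proof-of-efficacy criterion is affected.

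**What to change.** In SAP Table 2-1:
- Add an EOT row, with the EOT visit date as target and a window from that date to EOT + 7. Use the ECOG recorded at the EOT visit, including one taken on the day of surgery provided it precedes the operation. Closing the window the day before surgery would lose such a value.
- End the Week 3 window before the EOT visit. If C2D1 and EOT fall on the same date, assign each value by its nominal visit.
- Leave follow-up 1 starting at EOT + 8.

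Also reconcile the scope statements: SAP 2.1.3.11 says the windows serve longitudinal analysis as well, while SAP 2.7.4.3 limits them to the by-visit summary.

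The cost is one table row, one additional time point in the output and a short wording change. No new data are needed and trial conduct does not change.
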